7.3.1 Method of implementing the randomisation/allocation sequence

The allocation lists will be generated by the trial statistician and uploaded for use in the RRAMP system. Full details of the randomisation blinding plan and schedules will be documented and stored in the confidential statistical section of the eTMF.

7.4 Blinding

The patients and the assessors of primary and secondary outcomes (trained physiotherapists, rehabilitation doctors) will be blinded to trial treatment arm. Baseline AMS is assessed at presentation, prior to randomisation. When randomised, the patient will not be informed which trial arm they have been allocated to. At around 2 – 3 months post-surgery patients are transferred from the MTC, where the surgery was done, to a spinal injuries unit for rehabilitation. The 6 months post-randomisation assessment will be performed by a physiotherapist or rehabilitation doctor based at the spinal injuries unit, on a different site from the MTC where the surgery was done, that has no access to the notes from the original hospital other than, in some cases, the transfer letter.

We intend to instruct surgeons and physiotherapists, in the initial site visit, to state that the patient was part of the DISCUS trial, but not state details of the surgery that was performed.

We are confident that the physiotherapist or clinician that performs the 6-month assessment will not seek to un-blind themselves by seeking details from the MTC about the type of surgery that was performed. It is unlikely that the assessor becomes accidentally unblinded; in this case, the assessor will state the unblinding and the data will still be used. The study will report the number of unblinded assessments that have been performed.

7.5 Emergency Unblinding

Though this is applicable to drug trials, we do not foresee any situation that a patient recruited into DISCUS will require emergency unblinding.

7.6 Data to be recorded

All patients will have a medical history taken and a clinical examination as part of the routine standard care. The following are to be recorded in part I of the case report form (CRF):

ELIGIBILITY DETAILS:

- 1) Numbers screened, eligible, approached and recruited to the trial and all reasons for not being eligible, approached or recruited.
- 2) Informed consent process
- 3) Obtained consent or authorisation for enrolment

PATIENT DETAILS:

- 4) Patient demographics (ethnicity)
- 5) Co-morbidity at baseline according to the Charlson Index [Charlson et al., 1987].
- 6) Methylprednisolone administration

INJURY DETAILS:

- 7) Injury details (Date / time, Mechanism (road traffic accident, assault, fall, sport, other), Spinal level (C1-T1), upload ISNCSCI chart)
- 8) Pre-operative status (Heart rate, blood pressure, list other injuries)
- 9) Imaging review (MRI + CT). Note CT is done before the patient has entered DISCUS as part of standard of care; DISCUS does not request for this CT to be done but, if the scan is available, then DISCUS will use some information from this scan

The following details will also be recorded:

SURGERY DETAILS:

- 10) Surgery (Date / time, Approach: Posterior versus anterior+posterior, No. of levels laminectomised, Make of Duroplasty, Length / width of duroplasty patch (cm), Duration of surgery (minutes skin to skin), Estimated blood loss during surgery, American Society of Anaesthesiologist (ASA) grade

MECHANISTIC STUDY:

- 11) Pressure probe: Date inserted, date removed
- 12) Microdialysis probe: Date inserted, date removed
- 13) Hourly ISP, MAP, MD (glucose, lactate, pyruvate, glutamate, glycerol)
- 14) Recording and daily upload of hourly pressure probe readings – for 5 days post operation
- 15) Recording and daily upload of hourly microdialysis readings – for 5 days post operation
- 16) Cytokine assay results

POSTOPERATIVE (for up to two weeks after surgery):

- 17) List of operations for other injuries
- 18) ICU: no. of days stay

- 19) Imaging review (MRI)
- 20) CSF: CSF leak (yes/no), Pseudomeningocele (yes/no), lumbar drain (date inserted, date removed), re-operation for CSF leak (yes/no)
- 21) Pressure ulcers (yes/no)

SPINAL INJURIES UNIT (REHABILITATION):

- 22) Date of transfer to Spinal Injuries Unit
- 23) Date of Discharge from Spinal Injuries Unit
- 24) Name and address of rehabilitation centre

7.7 Trial assessments

Clinical assessments: Patients are admitted to neurosurgery units in MTCs where initial investigations, management and assessments are made. Screening against the eligibility criteria and approach for recruitment into DISCUS will be from an appropriate professional (e.g. neurosurgery or ICU specialist trainee, neurosurgery or ICU consultant, nurse, physiotherapist). Most importantly, for the computation of the primary outcome measure (Δ AMS) is completion of the AIS chart, which is routinely done in these patients at baseline (by physiotherapist, intensivist or neurosurgeon) and 6 months (physiotherapist or rehabilitation doctor). The ISNCSCI is standard and widely used. CUE-Q tests upper limb function, a dynamometer will be used to quantify grip strength, WISCI-II assesses walking ability and SCIM-III evaluates self-care and daily living including sphincter function and are all validated and routinely performed in TSCI patients by physiotherapists or rehabilitation doctors at spinal injury units. For a detailed description of these assessments, see the Spinal Cord Injury Research Evidence website [SCIRE Professional, 2016].

HRQoL assessments: The HRQoL assessments at 6 and 12 months will be sent to participants either by email or completed by telephone call from SITU, depending on patient preference. These assessments are valid to be administered by phone.

The schedule of trial assessments and methods for data collection is described in Table 1, below:

TIMEPOINT	DATA	DATA COLLECTION METHOD
Baseline	
 • Patient characteristics • AIS (motor, light touch, pinprick, grade) • MRI scan • CT scan 	
 • AIS completed by neurosurgeon, intensivist, physiotherapist • NIHR research nurse/local clinical team
Surgery within 72 hours of TSCI		
1-14 days post-operative	
 • Reoperations including procedure specific complications • Serious adverse events • MRI: compressed cord length, size of pseudomeningocele • Samples for mechanistic study if participating 	
 • NIHR research nurse/local clinical team • P.I. neuroradiologist • MD samples • Reported SAEs and listed procedure-specific complications

6 months from randomisation	
 • AIS (motor, light touch, pinprick, grade) • HRQoL (SF-36) • CUE-Q, WISCI-II, SCIM-III, grip strength • Length of hospital stay • Re-operations on spine including procedure specific complications • MRI: cord tether, syrinx, spinal deformity, size of pseudomeningocele • Serious adverse events 	
 • HRQoL completion, patient/carer will self-complete in clinic or via email/ phone call or by post • AIS, CUE-Q, WISCI-II and SCIM-III assessments completed by physiotherapist, rehabilitation doctor • NIHR research nurse/local clinical team • P.I. neuroradiologist
12 months from randomisation	
 • HRQoL (SF-36) • Mortality • Reoperations (including procedure specific complications) • Serious adverse events 	
 • Completion via email or by phone call or by post, from hospital notes or from GP. • Reported SAEs and listed procedure-specific complications

Imaging assessments: MRI and CT images will be transferred by image exchange portal (IEP) or otherwise to St. George's Hospital for analysis. The preoperative CT is done **before the patient has entered DISCUS** as part of standard of care. DISCUS does not request for this CT to be done but, if the scan is available as standard of care, then DISCUS will use some information from this scan. IEP is a web-based application that allows healthcare professionals to securely transfer patient images from one hospital to another. NHS and private hospitals have been using IEP since January 2010. Transfer of images by IEP is the preferred method of image transfer rather than CD to maximise data protection and improve patient management by ensuring the images are from the PACS (Picture Archiving and Communication System) of the source hospital to the PACS of the destination hospital. PACS is the standard medical imaging technology used to securely store and digitally transmit electronic images and clinically relevant reports that eliminates the need to manually file and store, retrieve and send sensitive information, films and reports. Pre-operatively, we will record cause of injury, level of injury, surgical approach and type of injury (as per AO sub-axial classification system A, B, C, F to be done by the neuroradiology P.I. based on CT). From the MRI done within 2 weeks of surgery, we will note how well the cord is decompressed i.e. the length of cord on T2 mid-sagittal view without CSF in front and behind it as well as size of pseudomeningocele. We will measure the cranio-caudal (height), antero-posterior (length) and medio-lateral (width) lengths of the pseudomeningocele using the T2 sagittal and axial MRI sequences, and estimate its volume as (height x width x length / 2). It is vital to record MRI features at 6 months including cord tethering (i.e. whether there is CSF around the cord) to the surrounding dura which is expected to reduce with duroplasty as more space is created around the cord as well as size of pseudomeningocele to be determined as described above.

A major problem with TSCI patients is delayed syrinx formation and therefore the size of syrinx (cranio-caudal length on T2) will also be assessed using the 6 month MRI. Finally, we will assess deformity at 6 months to make sure that duroplasty does not lead to kyphosis.

Assessment of complications: Complications will be recorded post-operatively and at clinic visits and will be monitored and reported by the sites. We will record at 6 and 12 months the number of re-operations on the spine to ensure that duroplasty does not lead to further operations related to CSF leak or wound infection, though based on known safety data, we think this is unlikely. We will also record the length of hospital stay, which may reduce if duroplasty is beneficial, but may be confounded by availability of rehabilitation beds. Adverse events and complications relating to surgery will be recorded and reported by the sites.

Mechanistic assessments: From the monitoring to be performed for up to 5 days after surgery, we will assess mean daily ISP, SCPP, glucose, lactate, pyruvate, LPR, glutamate and glycerol. As there is no

consensus or evidence on what are considered normal ISP/SCPP/metabolite values, it is not ethical to alter treatment based on these values.

We will explain this to PIs during site visits and in the training videos. Once metabolites have been measured on site, the MD vials will be coded by patient number and day from injury and stored at -20 °C and periodically shipped to [name] at City St. George's, University of London for analysis of inflammatory markers to compute mean daily GRO α , IL1 α , IL1 β , IL4, IL8, IL10, IP10, MCP1, MIP1 α and MIP1 β .

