Trial Design	Randomised, controlled, double-blind, multi-centre, superiority
Trial Participant Population	Acute, severe, traumatic spinal cord injuries (TSCI)
Eligibility Criteria:	
Inclusion:
 
 1. Age \geq16 years; 2. Severe cervical (C2 – T1) TSCI (AIS grade A–C); 3. Deemed to require and be suitable for surgery that includes laminectomy by local surgeon; 4. Surgery within 72 hours of TSCI; 5. Able to provide informed consent (except in emergency) or consultee declaration or nearest relative/guardian or welfare attorney (proxy consent). 
Exclusion:
 
 1. Probable dural tear due to TSCI; 2. Life-limiting or rehabilitation-restricting co-morbidities; 3. Thoracic or lumbar TSCI; 4. Other central nervous system (CNS) disease
Planned Sample Size/Target	For UK recruitment only, the planned sample size is N=222 (85% power, 95% significance level). The planned sample size target may be increased to N=260 (90% power, 95% significance) depending on recruitment rate from international sites.
Treatment duration	10 – 15 minutes (to perform expansion duroplasty) 5 – 10 minutes (to insert ISP and MD probes)
Recruitment duration	6 years
Follow up duration	12 months
Planned Trial Period	1 January 2021 – 31 December 2028
Objectives	Outcome Measures
Primary To determine if the addition of duroplasty to bony decompression improves motor outcome after TSCI	Change in AIS motor score (6 months post-randomisation minus pre-operative baseline)

Secondary
 
To determine if the addition of duroplasty to bony decompression:
 
 1. Improves functional outcomes after TSCI 2. Improves quality of life after TSCI 3. Is safe 4. Improves MRI features 5. Improves physiology, metabolism and inflammation at injury site 	
 1. AIS (light touch, pinprick, grade) at 6 months; CUE-Q, grip strength, WISCI-II, SCIM-III at 6 months 2. SF-36 at 6 and 12 months 3. No. of re-operations on spine at 12 months; Complications, adverse events, mortality and length of hospital stay all at 12 months 4. Cord tether, syrinx, spinal deformity at 6 months 5. ISP, SCPP; Injury site glucose, lactate, pyruvate, glutamate, glycerol, LPR; Injury site cytokines
---	---

iv. ROLES AND RESPONSIBILITIES OF TRIAL MANAGEMENT COMMITTEES/GROUPS & INDIVIDUALS

Trial Management Committees

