C	Motor Incomplete	Motor function is preserved at the most caudal sacral segments for voluntary anal contraction OR the patient meets the criteria for sensory incomplete status by light touch, pin prick or deep anal pressure, and has some sparing of motor function more than three levels below the ipsilateral motor level on either side of the body. <50 % of key muscle functions below the level of injury have muscle grade ≥ 3 .
D	Motor Incomplete	Motor incomplete as defined above, with ≥ 50 % of key muscle functions below the neurological level of injury having muscle grade ≥ 3 .
E	Normal	Sensation and motor function graded as normal in all segments.

SECONDARY OUTCOMES (FUNCTION):

4. CUE-Q (to assess upper limb function) at 6 months.
5. Hand grip strength using a dynamometer at 6 months.
6. WISCI-II (to assess walking ability) at 6 months.
7. SCIM-III (to assess self-care and daily living) at 6 months.

SECONDARY OUTCOMES (QUALITY OF LIFE):

8. SF-36 at 6, 12 months.

4. – 8. are standardised tools. We will use these functional scales, which are established in TSCI, to confirm that the motor improvement that we seek is associated with functional improvements: CUE-Q (hand function), grip strength, WISCI II (walking) and SCIM III (independence measure that includes sphincter function and validated in TSCI). In addition, we use one a HRQoL scale as a secondary outcome measure (SF-36,) aiming to show that the functional improvement translates to improvement in HRQoL.

SECONDARY OUTCOMES (SAFETY)

9. Number of re-operations required on the spine within 12 months
10. Total length of hospital stay (Stay in MTC, stay in spinal injury unit, other hospital admissions)
11. Surgical complications and adverse events – recorded postoperatively and at follow-up visits
12. Overall survival (OS) – time from randomisation to death or end of follow-up (1 year)
13. MRI 2 weeks: Size of pseudomeningocele
14. MRI 6 months: Spinal deformity (Cobb angle between superior C2 and inferior C7 endplates); Size of pseudomeningocele,

9. – 12. are objective measures that yield the same value independent of assessor. 14. (spinal deformity) Is a standardised tool. Safety of duroplasty will be assessed in different ways, not only by comparing complications and adverse events, but also by determining the number of re-operations on spine, total hospital stay, OS as well as spinal deformity in the duroplasty versus the non-duroplasty arms.

SECONDARY OUTCOMES (MECHANISM):

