SECONDARY 4: To determine if bony + dural decompression improves MRI features, improves cord perfusion and reduces cord inflammation at the injury site.	MRI length of cord compression (no CSF around the cord in mid-sagittal MRI)	2 weeks
	MRI size of pseudomeningocele (cranio-caudal, antero-posterior, medio-lateral lengths, and estimated volume)	2 weeks, 6 months
	MRI Length of cord tether in mid-sagittal MRI	6 months
	MRI Mid sagittal length of cord syrinx	6 months
	Pressure monitoring at injury site: mean daily ISP (mechanistic study patients only)	Up to 5 days after surgery
	Pressure monitoring at injury site: mean daily SCPP (mechanistic study patients only)	Up to 5 days after surgery
	MD monitoring at injury site: mean daily glucose, lactate, pyruvate, LPR, glutamate, glycerol (mechanistic study patients only)	Up to 5 days after surgery

	MD monitoring at injury site: mean daily cytokines (GRO α , IL1 α , IL1 β , IL4, IL8, IL10, IP10, MCP1, MIP1 α , MIP1 β) (mechanistic study patients only)	Up to 5 days after surgery
SECONDARY 5: To determine if bony + dural decompression is safe.	Number of re-operations on spine	12 months
	Total hospital stay	12 months
	Complications and adverse events	12 months
	Overall survival (OS): from randomisation to death or end of follow-up	12 months
	MRI Spinal deformity: Cobb angle between superior C2 and inferior C7 endplates	6 months

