7.11 Loss to follow-up

Loss to follow up is defined as no response received in 3 consecutive separate attempts to contact a participant. Loss to follow-up is expected to be low but, at discharge from recruiting centre a family member/friend will be identified who can be contacted if the participant is too sick to respond to the questionnaires. The primary outcome, measured at 6 months, falls within the period that patients are still inpatients within spinal cord injury units, which further minimises loss to follow-up.

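### Total hospital stay is a 12-month outcome, but the protocol schedules its collection only at 6 months, so the 12-month figure may be incomplete

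*Protocol*

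**What the plan says.** The outcome and its time point are stated consistently in two places. The trial summary lists "mortality and length of hospital stay all at 12 months". In the table of objectives and time points in section 3.5, "Total hospital stay" stands under the safety objective with 12 months as its time point. Section 3.3 defines the content: "Total length of hospital stay (Stay in MTC, stay in spinal injury unit, other hospital admissions". The measure is therefore a sum over all inpatient periods, and is not confined to the first episode.

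The collection schedule says something else. Table 1 in section 7.7 puts "Length of hospital stay" in the 6-month row. The 12-month row holds SF-36, mortality, serious adverse events and "Reoperations (including procedure specific complications"; hospital stay is absent. The schedule of procedures in Appendix 2 has no line for hospital stay at any visit.

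On where patients are at 6 months, section 7.11 argues that loss to follow-up will be low because the primary outcome visit "falls within the period that patients are still inpatients within spinal cord injury units".

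Three other sections bear on collection. Section 7.6 (items 22 and 23) records the dates of transfer to and discharge from the spinal injuries unit, without a time limit. Section 11.1 takes length of stay from hospital records, the patient or both, without a time point. Section 9.3 lists readmissions among the events collected as outcomes, and Appendix 2 has complications recorded at day 14 and at months 3, 6 and 12.

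**The concern.** A cumulative outcome defined to 12 months needs a collection point at or after 12 months. Table 1 gives one at 6 months only, and by the protocol's own account many stays are unfinished then. The omission does not look like a general feature of the 12-month row: re-operations, serious adverse events and SF-36 appear in both the 6-month and 12-month rows, and stay does not.

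What is at stake is whether the trial can report the outcome it has named. If some sites update the stay after 6 months and others do not, the variable will mix stays complete to 12 months with stays closed at about 6 months, and the analyst may be unable to tell them apart. Section 7.7 expects that stay may fall if duroplasty helps. A comparison built on stays cut at 6 months could not show a difference that arises from discharges after that point.

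**Working it through.** The protocol states no figure for stay, so there is nothing to reproduce. The check sets the sections side by side.

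**1. Time point of the outcome.** Trial summary: 12 months. Section 3.5 table: 12 months. These agree.

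**2. Time point of collection.** Table 1: 6 months only. Appendix 2: no row. Section 7.7, text on complications: stay will be recorded, with no time point; the sentence follows one that sets re-operations at 6 and 12 months but does not itself carry those times. Section 11.1: no time point. No section schedules stay at 12 months.

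**3. Period without scheduled collection.** Follow-up is 12 months and the scheduled collection is at 6 months, so 12 − 6 = 6 months are not covered.

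**4. Each component of the outcome, taken in turn.**

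- *MTC stay.* Section 7.4 puts transfer to the spinal injuries unit at around 2 to 3 months after surgery. For patients on that path the MTC stay has ended before 6 months, and the transfer date in section 7.6, item 22, marks its end. No gap.
- *Spinal injuries unit stay.* Section 7.11 has patients still in the unit at 6 months. The discharge date in section 7.6, item 23, closes the stay if it is entered when it occurs. It has no 6-month limit, but no visit is attached to it, so a field still blank at 6 months is not brought back to the site at 12 months. Recoverable, but not prompted.
- *Other admissions, months 6 to 12.* Section 9.3 collects readmissions and Appendix 2 has complications recorded at month 12, so the occurrence of a readmission should be known. No section asks for its dates or number of days. This component cannot be computed from what the protocol says is recorded.

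**5. Size.** Suppose Table 1 alone were followed. A patient in hospital throughout the first 6 months would have about 6 months recorded, against a true 12-month total anywhere between 6 and 12 months. The shortfall for that patient lies between 0 and 12 − 6 = 6 months. For a patient discharged before 6 months, it equals the readmission days in months 6 to 12. Going from these bounds to a mean shortfall, or to a bias between arms, needs the proportion discharged by 6 months, the distribution of stay and the readmission rate. The protocol gives none of these.

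**The case against.** The strongest reply is that Table 1 is not the only instruction on data collection. Section 7.6 holds items that Table 1 lacks, including the spinal unit dates. Section 11.1 names hospital records as a source, and these can be consulted at any time. The 12-month row of Table 1 already draws on hospital notes and the GP. If the discharge date is entered whenever it occurs, the longest open component at 6 months is complete.

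This stands as far as it goes. A reader might infer from Table 1 and section 7.11 that hospital stay will be truncated at 6 months. The documents do not support that: truncation is a risk for sites that work from Table 1, not a consequence of the protocol as a whole. The reply leaves two gaps: there is no 12-month prompt, and the length of later readmissions is not asked for. Section 7.8 seeks consent to routine hospital data, but for follow-up beyond the trial's 12 months, so it does not fill either gap.

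A reader might also infer that an early death will be scored as a short, favourable stay. Section 10.3.3 gives general methods for continuous outcomes and does not mention hospital stay or deaths within it. Section 10.3 leaves the full analysis to a separate plan that is not at hand. Nothing is stated wrongly on this. Overall survival is reported separately, and section 10.1 expects 2 to 3% mortality by 6 months, which is 0.02 × 222 = 4.4 to 0.03 × 222 = 6.7 patients over both arms.

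Finally, section 7.7 itself warns that stay may be confounded by the supply of rehabilitation beds. That limits the weight the outcome can carry, but it is no reason to collect it incompletely.

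**Conclusion.** The mismatch is real. Total hospital stay is named twice as a 12-month outcome, is scheduled for collection only at 6 months, and has no row in Appendix 2. As written, the protocol allows the spinal unit stay to be completed but does not prompt it, and it does not ask for the duration of readmissions in months 6 to 12. The 12-month outcome may therefore be incomplete, to a degree that varies between sites.

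The point is minor. It concerns one secondary safety outcome and has no bearing on the primary analysis or the sample size. The size of any truncation cannot be derived from the protocol; only the bound of 0 to 6 months for a patient in hospital throughout the first 6 months follows from the schedule. The conclusion rests on the protocol text alone and assumes that no case report form or site instruction outside it already requests stay at 12 months. If one does, the protocol text still needs to be brought into line.

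**What to change.** Add length of hospital stay to the 12-month row of Table 1 and give it a row in Appendix 2. Word it as total inpatient days to 12 months, including any spinal unit discharge date still open at 6 months and the admission and discharge dates of each readmission. Align the wording with section 7.6, items 22 and 23, so that the same dates serve both. The 6-month entry can stay as an interim record. The outcome keeps its present definition, so no endpoint changes.

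The cost is one extra item at the 12-month contact, which already takes place by email, phone, post, hospital notes or GP, together with the matching protocol wording. For patients already past 12 months, sites would need to check hospital records for open discharge dates and readmissions. Making the change now keeps that retrospective work small, since the latest amendment has extended recruitment by 24 months.
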